5.1.2 Secondary Endpoints

The secondary endpoints related to the efficacy endpoints will be ORR and DOR by mRECIST based on investigator review.

The following efficacy endpoints by mRECIST (based on investigator review and IIR) and RECIST1.1 (based on IIR) are also the secondary endpoints in this study:

- PFS
- TTP
- TTR

OS is also the secondary endpoint in this study.

These efficacy endpoints are defined as follows.

- **ORR** is defined as the proportion of subjects who have best overall response (BOR) of complete response (CR) or partial response (PR) at the time of data cutoff.
- **DOR** is defined as the time from the first documentation of CR or PR to the date of first documentation of disease progression or death (whichever occurs first), in subjects with confirmed CR or PR.
- **PFS** is defined as the time from the first study dose date to the date of first documentation of disease progression or death (whichever occurs first).
- **TTP** is defined as the time from the first study dose date to the date of first documentation of disease progression.

- **TTR** is defined as the time from the date of first study dose to the date of first documentation of CR or PR, in subjects with confirmed CR or PR.
- **OS** is measured from the date of first study dose until date of death from any cause. Subjects who are lost to follow-up and the subjects who are alive at the date of data cutoff will be censored at the date the subject was last known alive or the cut-off date, whichever comes earlier.

Responses of PR or CR should be confirmed no less than 4 weeks after the initial response in this study. In order for stable disease (SD) to be considered the BOR, it must occur ≥ 5 weeks following the first dose of study drug.

Determination of the PK profile of lenvatinib and pembrolizumab while subjects are receiving combination therapy.

Serum ADA will be also measured for pembrolizumab.

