5.2.2 Subject Disposition

For the summary table of screening subjects, the number (percentage) of subjects who signed informed consent, continued in the study after screening, failed screening, and the primary reason for screen failures will be presented.

The number (percentage) of subjects who were treated will be provided by country and site.

For the summary table of the subject disposition on study treatment, the number (percentage) of subjects who were treated, continued or discontinued study treatment at the time of study cutoff date, along with the primary reason for the study treatment discontinuation will be presented. The number (percentage) of subjects who discontinued treatment but were on survival follow-up at the time of data cutoff will also be provided.

For the summary table of the subject disposition on study, the number (percentage) of subjects who were on study or off study (ie, discontinued study) and the primary reason for study discontinuation will be presented.

Subject data listings will be provided.

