5.4.2 Secondary Efficacy Analyses

ORR and DOR by mRECIST based on investigator review will be analyzed in same manner as primary efficacy analysis.

The calculation of PFS, TTP, TTR and OS is as follows:

- PFS (days) = Date of first documented PD or death – date of first study dose + 1.
- TTP (days) = Date of first documented PD – date of first study dose + 1.
- TTR (days) = Date of first documented CR or PR – date of first study dose + 1.
- OS (days) = Date of death from any cause – date of first study dose + 1.

For a subject without an event of any of the above endpoints, the corresponding censoring date for that endpoint will be used in the above related calculation. The censoring rules for PFS, TTP and OS are detailed in [Section 8.2](#).

The analysis for PFS, and TTP by mRECIST (based on investigator review and IIR) and RECIST1.1 (based on IIR), and OS will be performed in all subjects and summarized in same manner as DOR. TTR will be summarized using descriptive statistics only for the subjects with confirmed CR or PR.

Subject data listings will be provided.

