 - PR, PR, two missing scans, PR, PD, then DOR has an event at the PD date (instead of the censoring at the second PR based on the primary analysis)
- etc.

Censoring rules for OS

No.	Situation	Date of Event (Death) or Censoring	Outcome
1	Death before or on data cut-off	Date of death	Death
2	Death after data cut-off	Date of data cut-off	Censor
3	Alive at data cut-off	Date of data cut-off	Censor
4	Lost to follow-up or withdrawal of consent before data cut-off	Date last known to be alive	Censor

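### OS for subjects alive at data cutoff is censored by two different rules in SAP Sections 5.1.2 and 8.2

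*SAP*

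**What the plan says.** Section 5.1.2 defines OS and applies one rule both to subjects lost to follow-up and to those alive at cutoff: "the subjects who are alive at the date of data cutoff will be censored at the date the subject was last known alive", or at the cutoff if that is earlier.

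The OS table in Section 8.2 separates these groups. Row 3, "Alive at data cut-off", is assigned "Date of data cut-off" with no last-known-alive limit. The last-known-alive date appears only in row 4, "Lost to follow-up or withdrawal of consent before data cut-off".

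Section 5.4.2 links the analysis to the table: "The censoring rules for PFS, TTP and OS are detailed in" Section 8.2. It does not say that the table overrides Section 5.1.2.

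Section 5.2.2 plans a count of subjects who "discontinued treatment but were on survival follow-up at the time of data cutoff", so subjects in survival follow-up at that date are expected. Section 5.4.1 sets the cutoff at 31 Oct 2019.

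**The concern.** The two sections name the same group and give it different dates. The SAP does not define alive at data cutoff. If it means that no death is recorded, row 3 credits a subject with time after the last contact during which nobody observed whether the subject was alive. If it means confirmed alive at or after the cutoff, a subject still in follow-up but last contacted earlier fits no row of the table.

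Two programmers working from different sections could therefore produce different Kaplan-Meier OS curves from the same data, and neither would have departed from the SAP. Section 10 allows double programming, so such a mismatch could arise in practice.

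The direction of error depends on how deaths are reported:

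- The cutoff rule overstates OS to the extent that deaths between last contact and cutoff are missed.
- The last-known-alive rule understates OS if those deaths are captured but survivors' contact dates are not brought forward.

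**Working it through.** **The rules side by side**

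| Subject with no recorded death by cutoff | Section 5.1.2 | Section 8.2 table |
|---|---|---|
| Lost to follow-up before cutoff | last known alive | last known alive (row 4) |
| Contacted alive on or after cutoff | cutoff | cutoff (row 3) |
| Still in follow-up, last contact before cutoff | last known alive | cutoff (row 3), or no row at all if alive means confirmed alive |

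Only the third line conflicts.

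**One subject.** Following Section 5.4.2, OS time = censoring date − first dose date + 1. Assume first dose on 31 Oct 2018, with the cutoff at 31 Oct 2019.

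- Row 3: 365 + 1 = 366 days, whatever the last contact date.
- Section 5.1.2, last contact 8 Aug 2019 (84 days before cutoff): 281 + 1 = 282 days.
- Section 5.1.2, last contact 19 Sep 2019 (42 days before cutoff): 323 + 1 = 324 days.
- Section 5.1.2, last contact on or after 31 Oct 2019: 366 days, so the rules agree.

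**Effect on 12-month OS.** The SAP states no figure to reproduce, and the inputs below are assumptions apart from the 80 subjects of the primary efficacy population. OS is exponential with median 15, 20 or 25 months. Follow-up is uniform on 6 to 12 months for half the subjects and on 12 to 30 months for the other half. The gap from last contact to cutoff is uniform on 0 to 1.4 or 0 to 2.8 months (about 6 or 12 weeks). The share of deaths in the gap that reach the database is 0, one half or 1. There were 4,000 simulated trials per setting.

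The true 12-month OS is 0.5^(12/median): 0.574, 0.660 and 0.717. Mean Kaplan-Meier estimates are shown as cutoff rule / last-known-alive rule:

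| Median (months) | Gap up to (months) | No gap deaths captured | Half captured | All captured |
|---|---|---|---|---|
| 15 | 1.4 | 0.587 / 0.574 | 0.582 / 0.569 | 0.575 / 0.562 |
| 15 | 2.8 | 0.598 / 0.572 | 0.587 / 0.560 | 0.575 / 0.548 |
| 20 | 1.4 | 0.673 / 0.662 | 0.664 / 0.653 | 0.662 / 0.651 |
| 20 | 2.8 | 0.683 / 0.660 | 0.668 / 0.645 | 0.661 / 0.638 |
| 25 | 1.4 | 0.727 / 0.717 | 0.722 / 0.712 | 0.717 / 0.707 |
| 25 | 2.8 | 0.736 / 0.717 | 0.728 / 0.708 | 0.716 / 0.695 |

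- Difference between rules: from 0.727 − 0.717 = 1.0 point to 0.587 − 0.560 = 2.7 points. It hardly depends on the share captured.
- Cutoff rule against the truth: 1.0 to 2.4 points too high with no capture, 0.4 to 1.3 too high with half, within 0.2 with full capture.
- Last-known-alive rule against the truth: within 0.2 with no capture, 0.5 to 1.5 too low with half, 0.9 to 2.6 too low with full capture.
- Expected deaths in the gap: 1.0 to 2.8 per 80 subjects. The SD of the 12-month estimate is 5.4 to 6.3 points.

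A separate simulation used other assumptions: medians of 12, 18 and 24 months, follow-up uniform on 6 to 18 months, and all deaths captured. The cutoff rule gave a 12-month estimate 1.1 to 1.6 points higher with gaps up to 6 weeks, and 2.4 to 3.3 points higher with gaps up to 12 weeks.

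**The case against.** The strongest reply is that the rules can be read to agree. Row 2 of the OS table censors deaths after the cutoff at the cutoff, so the table already uses status learned afterwards. In that setting, row 3 may mean known to be alive at the cutoff. For such a subject, the earlier of the two dates in Section 5.1.2 is also the cutoff, and for lost subjects both sections give the last-known-alive date. This reading turns the conflict into a gap, because the subject in follow-up with an earlier last contact then has no row. It also leaves the Section 5.1.2 minimum with nothing to do for subjects alive at cutoff, which suggests that earlier contact dates were foreseen.

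A second reply is that Section 5.4.2 sends the programmer to the table, and Section 9 leaves derivation rules to separate documents, so the table would probably be used. That is likely, but it settles the matter by presumption, in favour of the rule that can credit unobserved time.

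Two further points stand. Whether any subject is affected depends on the contact schedule and on any status check at cutoff, neither of which is in the SAP; if status is updated to the cutoff, the effect is zero. And the simulation does not favour the last-known-alive rule in every case: with all gap deaths captured, row 3 is the unbiased rule. Changing the wording without updating contact dates could therefore move the bias rather than remove it.

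**Conclusion.** The inconsistency is real. Two current sections of the SAP censor OS differently for subjects without a recorded death who remain in follow-up and were last contacted before 31 Oct 2019. Reading row 3 as confirmed alive leaves those subjects without a rule. Confidence is high for the textual conflict. The numerical effect is illustrative only, because it rests on assumed contact gaps, survival and death capture.

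Under the main assumptions, the choice of rule moves 12-month OS by 1.0 to 2.7 percentage points, less than half the sampling SD. The direction of bias depends on death capture. OS is a secondary endpoint, Section 5.3.3 plans no statistical comparison, and the primary ORR and DOR analyses are untouched. The point is minor, but it should be settled before lock because the OS results enter the study report that supports the accelerated-approval application.

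**What to change.** State one rule in both sections. In row 3 of the Section 8.2 OS table, replace the cutoff date with the earlier of the last-known-alive date and the cutoff. Only subjects with documented survival status on or after the cutoff are then censored at the cutoff. This agrees with the OS definition in Section 5.1.2 and gives every subject still in follow-up a row.

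Before database lock, update deaths and last-known-alive dates together, as of the cutoff, for all subjects not lost or withdrawn. This step belongs with the wording change: once status is current to the cutoff, the two rules give the same date and neither is biased.

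The cost is one table cell, one line of derivation code and one survival-status update.

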8.3 Safety Data Handling

Definition of derived variables for extent of exposure

The derivation rule will be presented in the [Section 5.6.1](#).

Treatment-emergent adverse event

A treatment-emergent adverse event (TEAE) is defined as an AE that emerges during the time from the first dose of study drug (either lenvatinib or pembrolizumab, whichever earlier) to 30 days following the last dose of study drug (either lenvatinib or pembrolizumab, whichever later), having been absent at pretreatment (Baseline) or

- Reemerged during treatment or up to 30 days following the last dose of study drug, having been present at pretreatment but stopped before treatment, or
- Worsened in severity during treatment or up to 30 days following the last dose of study drug relative to the pretreatment state, when the AE was continuous.

Serious adverse events (SAEs) that develop from 31 days up to 120 days after the subject's last dose of study drug are considered as treatment-emergent SAEs.

TEMAV (Treatment-Emergent Markedly Abnormal Value)

The treatment-emergent markedly abnormal laboratory values (TEMAV) will be defined as the postbaseline value of Grade 3 or 4 with an increase of at least 1 CTCAE grade from baseline. TEMAV is derived as follows based on CTCAE grade.

If the baseline CTCAE grade is 0 (normal), 1 or 2, and the postbaseline CTCAE grade is 3 or 4 then the postbaseline value is considered a TEMAV. Or, if the baseline CTCAE grade is 3 or 4 and the postbaseline CTCAE grade is higher than the baseline CTCAE grade then the postbaseline value is considered a TEMAV.

Handling of below lower quantification values in laboratory results

In the cases where a laboratory result contains a value of below the limit of quantification (BLQ), it will be replaced with the lower limit value of quantification (LLOQ) for summary tables.

The priority of use for blood pressure

For systolic and diastolic blood pressures, an additional confirmatory assessment may be done more than 60 minutes after initial assessment, if necessary. In the case where there are both the initial and confirmatory assessment results in a day, the confirmatory (latest) one will be used.

Visit windows for safety analyses

In the calculation of descriptive statistics for safety parameters (eg, laboratory values and vital signs, etc.) per scheduled visit, and change from baseline per visit, if multiple observations fall in the same scheduled visit, the first record will be used for summary tables. Other safety analyses (eg, worst grade laboratory results) will include all observations until the date of 30 days following the last dose of study drug.

8.4 Pharmacokinetic Data Handling

8.4.1 Lower Limit of Quantification of lenvatinib Plasma Concentration and Everolimus Blood and Concentration

The LLOQ of lenvatinib plasma concentrations is 0.250 ng/mL

The LLOQ of pembrolizumab serum concentrations is 25 ng/mL

8.4.2 BLQ Handling for Calculation of PK Parameters

While calculating PK parameters in WinNonlin, BLQ values will be handled according to 302-104.00-MNL, for non-compartmental pharmacokinetic analysis.

8.4.3 BLQ Handling for Developing Concentration-Time Profiles

When developing individual concentration-time profiles, BLQ values will be handled according to 302-104.00-MNL for non-compartmental pharmacokinetic analysis.

8.4.4 Handling of Anomalous Concentration Values

The handling of anomalous concentration values will follow the guidance in the SWP for non-compartmental pharmacokinetic analysis (302-104.00-MNL).

8.4.5 General Rules for Presentation of Drug Concentrations and PK Parameters

When presenting individual/raw (raw, hereafter) values and summary statistics, the following rule will be applied: for drug concentrations and concentration-dependent pharmacokinetic parameters, all summary statistics (mean, median, geometric mean, SD and coefficient variation (CV)) will have 3 significant digits. For t_{max} , raw values and their median are shown in fixed 2 decimal places.

Variable	Unit	N	Digit rule	Raw/ Minimum/ Maximum	Mean Median	SD	Geometric Mean	CV (%)
drug concentration	ng/mL	X	Significant digits	3	3	3	-	-
C_{max} , $C_{ss,max}$, C_{min} , $C_{ss,av}$	ng/mL	X	Significant digits	3	3	3	3	3
t_{max} , $t_{ss,max}$	h	X	Fixed decimal places	2	2	-	-	-
λ_z (CID1&D15)	1/h	X	Significant digits	3 (Listing only)	-	-	-	-
$t_{1/2}$ (CID1&D15)	h	X	Significant digits	3	3	3	3	3
$AUC_{(0-t)}$, $AUC_{(0-inf)}$, $AUC_{(0-ti)}$, $AUC_{(0-\tau)}$	ng•h/mL	X	Significant digits	3	3	3	3	3
CL/F, CL_{ss}/F	L/h	X	Significant digits	3	3	3	3	3
V_z/F (CID1&D15)	L	X	Significant digits	3	3	3	3	3
R_{ac}		X	Significant digits	3	3	3	3	3
PTF ratio		X	Significant digits	3	3	3	3	3

Mean, SD, geometric mean and CV will not be calculated for t_{max} , $t_{ss,max}$.

$CV(\%) = \sqrt{(\exp[SD^{**2} \text{ of log transformed data}] - 1)} * 100$

NOTE

1. The following parameters are reported in the CSR, but appear in Listings only. They are important information to confirm that individual $t_{1/2}$ and its related parameters such as $AUC_{(0-inf)}$ are appropriately derived and allow those PK parameters to be reproduced when necessary.
 - a. Time points used for estimation of λ_z (lower and upper)
 - b. Number of the time points used for λ_z
 - c. Adjusted regression coefficient (R_{2adj})

In Listings, a) are shown in same digits as actual sampling time after dosing used for calculation of PK parameters. For b), integer number is used in Listings. For c), 3 significant digits are used in Listing.

9 PROGRAMMING SPECIFICATIONS

The rules for programming derivations and dataset specifications are provided in separate documents.

10 STATISTICAL SOFTWARE

All statistical analyses will be conducted by Eisai or Takumi Information Technology, using validated standard programs or double programming. For analyses needed in data review, single programming will be used.

All statistical analyses will be performed using SAS (version 9.3 or later). As necessary, other validated statistical software will also be used.

11 MOCK TABLES, LISTINGS, AND GRAPHS

The study TLG shells will be provided in a separate document, which will show the content and format of all tables, listings, and graphs in detail.

